8.11. Identification of Data to Be Recorded on Case Report Forms

The electronic case report form (eCRF) data will be entered from source documentation. No source data will be recorded directly in eCRF (i.e., without prior record of data). These data will be consistent with the source documents or the discrepancies will be explained. No personally

identifying data will be recorded on eCRFs. The investigator is ultimately responsible for the accuracy of data transcribed on the eCRF. Data monitoring and management will be performed in the electronic data capture (EDC) database system by the study monitor and the designated data management group. A detailed data management plan will be written and approved by the study team and the PI prior to study start. All updates to the data management plan must be approved before study closeout and database lock.

8.12. Known and Potential Risks and Benefits to Human Subjects

8.12.1. Risks/Discomfort to Subjects and Precautions to Minimize Risk

Outlined as follows are anticipated and unexpected adverse reactions with a brief description of procedures to ameliorate risks and symptoms. In general, dose escalation is being performed to ensure an acceptable safety record for IM administration of the vaccine product in this study. Prior to proceeding with the next dose in the next group of subjects, all safety data will be reviewed by the PSRT, and a determination will be made as to whether the study can continue to enroll subsequent cohorts (at the dose escalation planned) based on the observed safety record from the preceding dose level. In addition to this overall safeguard, individual risks will be closely monitored and any AEs will be quickly identified and managed.

8.12.1.1. Local Reactions

Local reactions at the vaccination site are expected from IM immunization. The IM route of vaccination, in general, has been shown to be a safe and effective route of administration. There may be some mild discomfort and irritation from an IM vaccination from the initial injection. These are typically mild and transient in nature. In addition, there is the possibility of local erythema, pruritus, swelling, and/or induration that appears over time. In addition, subjects may develop temporary swelling in the lymph nodes under the arm where vaccination occurred.

8.12.1.2. Systemic Reactions

Any vaccine may be associated with a wide range of systemic reactions, such as fevers, constitutional symptoms (fatigue, malaise, appetite change), and gastrointestinal symptoms (diarrhea, abdominal pain) as well as others to include allergic reactions (bronchospasm, urticaria, anaphylaxis). The frequency and type of systemic symptoms will be assessed and analyzed with respect to study product.

8.12.1.3. Pregnancy

During initial screening and prior to each vaccination, a urine pregnancy test will be performed. Subjects with a positive test will be excluded from the study. A final urine pregnancy test will be conducted during the last clinic visit. Female subjects of childbearing potential must agree to use an effective method of birth control (birth control pills, injection hormonal contraceptive, implant hormonal contraceptive, hormonal patch, IUD, sterilization by hysterectomy or tubal ligation, spermicidal products and barrier methods such as cervical sponge, diaphragm, or condom) during the study and 3 months following the last vaccination. Abstinence is acceptable. While female subjects will not be required to disclose their method of birth control, they will be counseled during the initial screening on acceptable forms of birth control required for study enrollment. At each visit, female subjects will be reminded that they must agree to use effective

contraception to remain in the study. Female subjects should not become pregnant during the study and for at least 3 months after the last vaccine dose.

8.12.1.4. Lactation

Risks to nursing infants are unknown at this time; breastfeeding females will be excluded from this study.

8.12.1.5. Venipuncture

Blood sampling carries a minimal risk of minor discomfort and the possibility of minor bruising at the site of the needle puncture and, rarely, the possibility of infection at the needle puncture site.

8.12.1.6. Allergic Reaction

As with any Investigational New Drug (IND) product administration and no matter what precautions are taken, there is always the risk of a serious, or even life-threatening, allergic reaction. Although anaphylactic reactions are not anticipated, as with any vaccination, the rare possibility exists. For this reason, all subjects will be observed at the study site (WRAIR CTC) for a minimum of 30 minutes following vaccine dosing. Appropriate emergency equipment (e.g., automated external defibrillator, air-shields manual breathing unit bag) and medication [e.g., antihistamines and adrenaline (epinephrine)] for initial treatment of an allergic reaction will be available at the WRAIR CTC whenever immunizations are given. This equipment is available to handle emergencies such as anaphylaxis, angioedema, bronchospasm, and laryngospasm. Existing staff standard operating procedures at the WRAIR CTC are also in place for these events.

8.12.1.7. Theoretical Risks

Post-infection reactive arthritis, characterized as an asymmetric, oligoarticular arthritis commonly involves the knees, ankles, or wrists is known to occur following *Shigella* infection. Some data suggests that the risk of reactive arthritis following shigellosis may be higher in persons carrying the Human Leukocyte Antigen (HLA)-B27 antigen [20]. There is enough uncertainty as to the etiology of arthritis, that a specific entry criteria related to this theoretical risk is included and will exclude volunteers with a personal or immediate family history of inflammatory arthritis or HLA-B27 positivity.

8.12.1.8. Unknown Risks

As with all research, there is the remote possibility of risks that are unknown or that cannot be foreseen based on current information. This would include late effects that have been seen with some vaccines.

8.12.2. Alternatives to This IND Product or Study

At this time, there are no known alternative, licensed vaccines directed at *Shigella*. An alternative choice is not to participate in this study.

8.12.3. Intended Benefit for Subjects

There is no benefit that can be guaranteed to volunteers for participating in this research study. However, there is potential societal benefit of the development of an effective *Shigella* vaccine.

8.12.4. Risks to Study Personnel and the Environment

The principal risk in the clinical setting is in the handling of needles that may be contaminated and the attendant risks including hepatitis, human immunodeficiency virus (HIV), and other human pathogens. Adherence to standard operating procedures (SOPs) for working with infectious agents and universal precautions will reduce the risk of exposure.

There are no known risks to the environment other than those associated with the generation of biohazardous waste attendant to vaccination of humans. All biohazardous waste will be disposed of as stipulated by local, state, and federal regulations and in accordance with study-site SOPs.

8.13. Route of Administration, Dosage Regimen, Treatment Period, and Justification

On days 1, 22, and 43 subjects will be administered Invaplex_{AR}-DETOX or placebo. Each subject will receive the same formulation at each vaccination dependent upon group assignment. Dose formulations will be prepared each day of immunization at the clinical site using the Invaplex_{AR}-DETOX drug product. Because Invaplex_{AR}-DETOX has not been previously administered to humans, limited information is available to estimate the dose needed to induce suitably robust immune responses while maintaining an acceptable safety profile. Guinea pigs have been immunized intranasally with 25 µg or intramuscularly with 1, 5, and 25 µg of cGMP Invaplex_{AR}-DETOX. The vaccine was well-tolerated and induced a robust immune response. This study is designed as a placebo-controlled, dose-escalating study starting with the lowest dose of Invaplex_{AR}-DETOX (2.5 µg) and progressing upwards through higher doses up to 25 µg. Following completion of each of the vaccination series, an interim safety report will be compiled and a dose-escalation decision will be made in concert with the PSRT. If the vaccine is safe and immunogenic, future studies will evaluate the preliminary efficacy of this vaccine using a homologous enteric *S. flexneri* 2a strain in a human challenge model. The overall goal of the current *Shigella* development plan is to create a broadly protective multivalent *Shigella* vaccine from a combination of Invaplex vaccines encompassing the conserved invasin proteins and the combination of serotype specific LPS for each proposed strain to integrate. The proposed multivalent vaccine would integrate the major *Shigella* serotypes responsible for human disease: *S. flexneri* 2a, *S. flexneri* 3a, *S. flexneri* 6, and *S. sonnei*.

8.14. Compliance Statement

The study will be conducted according to the protocol and in compliance with International Council on Harmonisation (ICH) Good Clinical Practice (GCP), Belmont Principles, and other applicable regulatory and DoD requirements. All identified study personnel will be trained to perform their roles and will carry out their responsibilities in accordance with ICH GCP guidelines and clinic site study procedures.

8.15. Study Population

In this initial study, it is important to restrict enrollment to a small number of healthy subjects without factors that may limit or confound assessment of AEs and vaccine-induced immune

response. The study population will consist of healthy male and nonpregnant, nonlactating female subjects, ages 18-50 years (inclusive), from the greater Washington, DC and Baltimore, Maryland areas, who can give informed consent and understand the risks and benefits of the study and are willing to comply with all protocol procedures and time commitments. A maximum of 60 subjects will be enrolled in this study. Four alternates per cohort may be asked to go to the clinic on vaccination days in the event a planned subject cannot/does not enroll in the study.

8.16. Study Site

The study will be conducted at the WRAIR CTC, Silver Spring, Maryland. Immunologic assays will be conducted at the subunit enteric vaccines and immunology laboratory of the WRAIR, Silver Spring, Maryland.

9. Selection and Withdrawal of Subjects

9.1. Recruitment of Subjects/Study Population

Healthy adults, both males and nonpregnant females, will be recruited from the Baltimore/Washington, DC, area through the WRAIR CTC by the use of advertisement in multiple media formats, to include but not limited to: newspapers, fliers, e-mails, the WRAIR CTC web site, public listservs, social media (such as Facebook), posters, bus ads, and generic radio advertisements. E-mail announcements and web site postings (e.g., WRAIR CTC) will include information found on recruitment scripts (excluding any compensation information) or posters excluding any photos unless attached as a complete flyer. Recruitment may also include oral presentations at events, meetings, and briefings wherein the desired recruit population might reasonably be expected to attend. All forms of recruitment, printed media, handouts, and briefs will have IRB approval prior to being used.

When a subject calls the WRAIR CTC recruitment office and discloses an interest in the study, the recruitment staff will discuss details of the trial from a prepared, IRB-approved script. If the subject is still interested, contact information will be obtained and an appointment for briefing/screening will be arranged.

Up to 60 subjects will be recruited for enrollment in this Phase 1 trial. Additionally, there will be up to 4 alternates recruited for each cohort.

9.2. Informed Consent Process

All subjects will undergo an informed consent process consisting of a detailed informational presentation of study-related material using a pre-recorded brief. Following the briefing, one of the study investigators will reiterate the purpose, procedures, and risks of the study as needed and answer any questions. This process will take place at the WRAIR CTC immediately preceding the screening procedures.

During the briefing session, an investigator or designee will brief prospective subjects using the briefing slides. The briefing may be provided by a pre-recorded slide set. An investigator will be available to answer any questions raised during the session. Following the briefing, the coordinator or designee will provide the subject with ample time to read the consent and will

answer any questions. The subject will be asked to sign the consent, as will the investigator conducting the informed consent discussion. The subject will be allowed to take the consent document home to consider and discuss it with others and can return it to the WRAIR CTC at a later time to sign it. After signing the consent (to include future use of specimens), the subject will take a comprehension test (“open book” format). Any questions missed will be explained to the subject, and the subject’s questions will be answered. The test is administered to aid study personnel in identifying gaps in understanding. If the subject appears not to understand the content of any of the questions, one of the study facilitators will be informed and must document whether the subject understands the risks, benefits, procedures, and time commitment as well as the answers to the questions that he or she missed. Any subject who, in the opinion of the PI, does not understand the study well enough to consider his or her consent truly informed will be excluded. The subject will be given one additional opportunity to take the comprehension test. A passing score of at least 70% will be required to participate in the study.

The informed consent process will include a recruitment script, briefing material, and an informed consent document. Throughout the study, all questions and concerns of the subject will be addressed. If the subject has additional concerns, the research monitor will be available to answer any medical questions, and the NMRC Office of Research Administration is available to answer any human use-related concerns.

No study procedures will occur before the subject provides written informed consent. Active duty military will not be specifically recruited for this study. Active duty military members interested in participating will need to obtain supervisor approval. To minimize any possible coercion, supervisors or anyone in the chain of command or in a dominant position will not be permitted to consent the subject.

9.3. Eligibility Screening

Each subject must meet all inclusion and no exclusion criteria. The PI or designee will make the final decision of the eligibility. Only eligible subjects will be given the investigational product.

9.4. Subject Inclusion Criteria

Subjects must meet all of the following criteria to be included in the study:

1. Healthy, adult, male or female, age 18 to 50 years (inclusive) at the time of enrollment.
2. Completion and review of comprehension test (achieved $\geq 70\%$ accuracy, two attempts allowed).
3. Provide written informed consent before initiation of any study procedures.
4. Agrees to complete all study visits and procedures and provide a screening stool sample.
5. Women of childbearing capacity: Negative pregnancy test with understanding (through informed consent process) to not become pregnant during the study or within three (3) months following the last vaccine dose.

9.5. Subject Exclusion Criteria

Subjects meeting any of the following criteria will be excluded from the study.

9.5.1. General Health

1. Health problems (for example, chronic medical conditions such as psychiatric conditions, diabetes mellitus, hypertension or any other conditions that might place the subject at increased risk of adverse events) – study clinicians, in consultation with the PI, will use clinical judgment on a case-by-case basis to assess safety risks under this criterion. The PI will consult with the Research Monitor as appropriate.
2. History of autoimmune disorders, cardiovascular and renal diseases.
3. Use of immunosuppressive medications (systemic corticosteroids or chemotherapeutics that may influence antibody development), or immunosuppressive illness, including IgA deficiency (defined by serum IgA <7mg/dL).
4. Women who are pregnant or planning to become pregnant during the study period plus 3 months beyond the last vaccine dose and currently nursing women.
5. Participation in research involving another investigational product (defined as receipt of investigational product or exposure to invasive investigational device) 30 days before planned date of first vaccination or anytime through the last in-clinic study safety visit.
6. Positive blood test for HBsAG, HCV, HIV-1/2.
7. Clinically significant abnormalities on basic laboratory screening (see section 8.1).
8. Systemic antimicrobial treatment (i.e., topical treatments are not an exclusion) within 1 week before administration of the first vaccine.

9.5.2. Research specific

9. Allergies that may increase the risk of AEs.
10. Regular use (weekly or more often) of antidiarrheal, anti-constipation, or antacid therapy.
11. Abnormal stool pattern (fewer than 3 stools per week or more than 3 stools per day) on a regular basis; loose or liquid stools on other than an occasional basis.
12. Personal or family history of inflammatory arthritis.
13. Positive blood test for HLA-B27 (associated with increased risk of reactive arthritis secondary to *Shigella* infection).
14. History of allergy to any vaccine.
15. Exclusionary skin disease history/finding that would confound assessment or prevent appropriate local monitoring of AEs, or possibly increase the risk of a local AE.

9.5.3. Prior Exposure to *Shigella*

16. Serum IgG titer > 2500 to *Shigella flexneri* 2a LPS.
17. History of microbiologically confirmed *Shigella* infection.
18. Received previous licensed or experimental *Shigella* vaccine or live *Shigella* challenge.
19. Travel to countries where *Shigella* or other enteric infections are endemic (most of the developing world) within two years prior to dosing (clinician judgment).

20. Occupation involving handling of *Shigella* bacteria currently, or in the past 3 years.

9.6. Subject Withdrawal Criteria

Each subject may withdraw consent at any time during the study without penalty. Counseling about the subject's health will be provided if he or she decides to discontinue participation in the study. Medical advice regarding what is in the best interest of the subject will be provided.

The PI may discontinue the subject's activity without the subject's consent if any of these criteria is met:

- A subject fails to comply with study procedures
- A subject's safety or health may be compromised by further participation
- It is determined to be in the subject's best interest

9.6.1. When and How to Withdraw Subjects

A subject may end his or her participation in the study at any time. If a subject withdraws, the investigator will make a reasonable effort to determine the reason for the withdrawal from the study and to complete termination procedures. Telephone calls, registered letters, and e-mail correspondence are considered reasonable effort. For subjects leaving the study, a targeted examination may be performed if medically indicated and if permitted by the subject.

A subject may be withdrawn for an AE or SAE resulting in a safety concern or for noncompliance with protocol requirements. When a subject withdraws or is withdrawn by the PI due to an AE that results in a safety concern, the sponsor must be notified within 72 hours. Investigators must follow specific policy at each institution regarding the timely reporting of AEs and SAEs to the local IRB (section 11.9.1.2). In all cases, the PI will make a reasonable effort to complete study termination procedures. Subjects who do not receive subsequent vaccine doses but who continue in follow-up for safety and immunogenicity are not considered to be withdrawn from the study.

If a subject meets withdrawal conditions for a concomitant medication violation or noncompliance, this should clearly be stated in the source document and the study termination eCRF.

9.6.2. Follow-up for Withdrawn Subjects

Attempts will be made to follow all subjects for safety up to 28 days after receipt of the last vaccine dose. Short-term safety follow-up 7-days post vaccination will also be attempted.

9.6.3. Data Collected for Withdrawn Subjects

All data collected up to the time of withdrawal will be reported, unless consent is withdrawn. If the subject proceeds with the specific follow-up procedures for withdrawn subjects, this data will also be collected and reported. The study termination eCRF will be completed with the reason for withdrawal specified.

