11.9.2.2. Adverse Event-related Withdrawal of Consent

Any AE-related withdrawal of consent due to a safety concern during the study must be reported *immediately* (within 72 hours of identification) by e-mail or fax to the sponsor and the NMRC IRB.

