12.1. Description of Statistical Methods

12.1.1. Analysis Addressing the Primary Study Objective (Safety Analysis)

The primary objective of this study is safety of the Invaplex_{AR}-DETOX vaccination. All immunized subjects will be included in the safety analysis. AE data will be listed individually and summarized by system organ class and preferred terms within a system organ class for each treatment group. Serious and/or unexpected AEs will also be discussed on a case-by-case basis. For the tabulation of AEs by system organ class, a subject will be counted only once in a given system organ class. For example, a subject reporting nausea and diarrhea will be reported as one subject, but the symptoms will be listed as two separate AEs within the class. Therefore, the total number of AEs reported within a system organ class may exceed the number of subjects within the system organ class reporting AEs.

Rates of all adverse events will be analyzed by Pearson's Chi-square test (or Fisher's exact test if assumptions are not met for Pearson's Chi-square), to compare groups, if applicable. Summary tables will be created to indicate the number of subjects who experienced events. Vaccine-related events (definitely, probably, or possibly related) will be tabulated by study group. In addition, tables will be prepared to list each adverse event, the number of subjects in each treatment group

who experienced an event at least once, and the rate of subjects with adverse event(s). Adverse events will be divided into defined severity grades (mild, moderate, severe, potentially life-threatening). The tables will also divide the adverse events by relationship to the investigational product if applicable. All immunized subjects will be included in the safety analysis.

Clinical and laboratory data regarding safety, which include vital signs and safety laboratory measures, will be included in the primary analysis. Changes in pulse rate, systolic and diastolic blood pressure, weight, and respiratory rate will be compared within each group and among groups using analysis of variance procedures. For hematology and serum chemistry tests, the mean, mean change, median, median change, and range of all values for each test for each treatment group at baseline and for the final “on therapy” values will be tabulated. The tables will also divide the adverse events into those considered at least possibly related to the vaccine and those considered not related.

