12.5. Selection of Subjects to Be Included in Analyses

All subjects who receive at least one dose of the investigational product will be included in the safety analyses. All subjects who receive at least two doses of the investigational product will be included in the immunological analyses.

13. Direct Access to Source Data/Documents

Subjects will be identified on eCRFs by a unique subject identification number and on source documents by name and date of birth. No personal identifier will be used in any publication or communication used to support this research study. The subject identification number will be used if it becomes necessary to identify data specific to a single subject. Representatives of the sponsor, the local IRB, and the FDA are eligible to review medical and research records related to this study as a part of their responsibility to protect human subjects in clinical research. Personal identifiers will be removed from photocopied medical and research records.

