6.3.1. Safety Population

The safety population will consist of all subjects who received at least one immunization. Subjects will be grouped according to the actual product received. This population will be used for all safety analyses. Denominators for different safety endpoints may vary according to the number of subjects with available data for the specific endpoint.

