6.5. Missing Data and Outliers

All attempts will be made to collect all data per protocol. As missing data are expected to be minimal, no imputation will be performed for missing values. Any data point that appears to be erroneous or inexplicable based on clinical judgment will be investigated as a possible outlier. If data points are identified as outliers, sensitivity analyses will be performed to examine the impact of including or excluding the outliers. Any substantive differences in these analyses will be reported. Non-analyzable data will be documented in the deviations.

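### Protocol 9.6.3 exempts data already collected from reporting when consent is withdrawn; this conflicts with the safety population in Protocol 12.1.1, 12.5 and SAP 6.3.1, and nothing says which rule prevails

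*Protocol*

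**What the plan says.** On data from subjects who leave:

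- Protocol 9.6.3: "All data collected up to the time of withdrawal will be reported, unless consent is withdrawn". The same section has the termination eCRF completed with the reason, and reports data from any follow-up procedures the subject goes on to complete.
- Protocol 9.6: "Each subject may withdraw consent at any time during the study without penalty".
- Protocol 9.6.1: a subject who stops vaccination but stays in follow-up does not count as withdrawn. A withdrawal caused by an AE that raises a safety concern goes to the sponsor within 72 hours.
- Protocol 11.9.2.2: "Any AE-related withdrawal of consent due to a safety concern during the study must be reported", within 72 hours, to the sponsor and the NMRC IRB.
- Protocol 9.6.4: subjects who leave after the first vaccination are not replaced.

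On who and what is analyzed:

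- Protocol 12.1.1: "All immunized subjects will be included in the safety analysis".
- Protocol 12.5: "All subjects who receive at least one dose of the investigational product will be included in the safety analyses".
- SAP 6.3.1: "The safety population will consist of all subjects who received at least one immunization", and "Denominators for different safety endpoints may vary according to the number of subjects with available data for the specific endpoint".
- SAP 6.5: "As missing data are expected to be minimal, no imputation will be performed for missing values".

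The SAP says nothing specific about data from subjects who withdraw consent.

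**The concern.** Safety is the primary objective, and the plan promises a safety analysis of everyone dosed. Section 9.6.3 opens a gap in that promise which can depend on the outcome. A reaction may lead a subject to withdraw consent, and withdrawal of consent is what triggers the exception. The protocol foresees this sequence, since 11.9.2.2 is devoted to AE-related withdrawal of consent.

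Two analysts could follow the documents in good faith and produce different primary tables from the same trial. One keeps the subject's graded events under 12.5; the other leaves them out under 9.6.3. With 16 vaccinees per dose group, a single record can decide whether an event type is reported as seen or not seen at that dose.

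**Working it through.** **Inputs.** There are 16 vaccinees in each of three dose groups, so 3 × 16 = 48 in all (Protocol Table 7). Safety proportions carry exact 95% intervals (SAP 8). The plan's own example is no events in 16, with an interval of 0-21% (Protocol 12.2, SAP 5). No dropout or consent-withdrawal rate is stated.

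**Step 1: reproduce the plan's figure.** The two-sided Clopper-Pearson upper limit for 0/n is 1 − 0.025^(1/n). For n = 16 this is 1 − 0.025^(1/16) = 20.6%, which rounds to the stated 21%. A one-sided 95% limit, 1 − 0.05^(1/16) = 17.1%, and the rule of three, 3/16 = 18.8%, do not match. The plan therefore uses the two-sided exact interval, and the same method is used below.

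**Step 2: set the rules side by side.** Protocol 12.1.1, 12.5 and SAP 6.3.1 define which subjects are in the safety set. Section 9.6.3 governs which of their data are reported. There are two ways to combine them:

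- The rules contradict each other. No passage ranks them, so the result depends on who applies them.
- Both are followed literally. The subject stays in the population but the events go unreported. SAP 6.3.1 then lets the denominator follow available data, and SAP 6.5 imputes nothing, so the SAP does not bring the events back.

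**Step 3: one assumed case.** One vaccinee in a group of 16 has a given event and withdraws consent; no one else in the group has it.

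- Data kept: 1/16 = 6.3%. The lower limit is 1 − 0.975^(1/16) = 0.2%. The upper limit is the 97.5th percentile of Beta(2, 15), 30.2%.
- Data dropped from numerator and denominator: 0/15 = 0%, with upper limit 1 − 0.025^(1/15) = 21.8%.
- Events dropped but subject still counted in N, as the Table 18 shell defines it: 0/16 = 0%, upper limit 20.6%. This is the same as the plan's no-event example.

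**Step 4: two reactors in a group.** With all data kept, 2/16 = 12.5% (CI 1.6-38.3%). If one withdraws consent and is dropped, 1/15 = 6.7% (0.2-31.9%). If both do, 0/14 = 0% (0-23.2%).

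**Step 5: how often this could arise.** For an assumed per-vaccinee probability p of withdrawing consent because of a reaction, the chance of at least one case is 1 − (1 − p)^n.

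- p = 1%: 15% in a group of 16; 38% among 48.
- p = 2%: 28%; 62%.
- p = 5%: 56%; 91%.
- p = 10%: 81%; 99%.

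These values of p are assumptions that show a range. They are not estimates.

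**The case against.** The strongest reply is that the analysis sections already settle the matter. Three passages keep every dosed subject in the safety analysis. The SAP never repeats the exception, not even in its section on removal of subjects (4.3.4). SAP 8.3 says that everything on the AE case report form goes into the listing, and Listing 1 shows who discontinued and why. On this reading 9.6.3 is loose wording that would never remove an event. It is a fair reading, and for that reason the documents do not support a reader's inference that such a subject disappears from the primary safety result. It does not close the point. Membership of a population does not restore events that another section exempts from reporting, and a discontinuation listing does not put graded events, diary entries or laboratory values into the summary tables.

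Three other stronger readings also fail:

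- *That the exception catches essentially every subject-initiated departure.* Section 9.6 uses the language of consent, but 9.6.1 speaks of ending participation, and 9.6.3 itself separates withdrawal from withdrawal of consent. Subjects who only stop doses, and those the investigator withdraws while consent stands, are outside it.
- *That the dose-escalation reports will lack these events.* SAP 6.6 bases the summaries on the safety population. AE-related withdrawals are notified within 72 hours, and the PSRT includes the principal investigator and the PATH medical officer. The PSRT would probably know of the event; whether the summary tables would count it is open.
- *That the safety result is biased toward safety.* The documents offer no evidence on who withdraws consent. Outcome-dependent loss is possible but not shown.

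The consent form might say what happens to data already collected. It is not in the text available here, so it cannot be assumed to resolve the conflict or to deepen it.

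**Conclusion.** The point stands as an unresolved conflict. Section 9.6.3, as worded, exempts data collected before withdrawal of consent from reporting. Protocol 12.1.1, 12.5 and SAP 6.3.1 point the other way, and no rule of precedence is given. Safety data from a vaccinee who reacts and withdraws consent can therefore be omitted from the primary tables; the documents do not show that they will be.

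The illustrated size is a change from 1/16 (6.3%) to 0/15 (0%) for one case in one dose group. This assumes that one reactor withdraws consent, that 9.6.3 is applied literally, and that the subject leaves both numerator and denominator. The intervals overlap widely (0.2-30.2% against 0-21.8%), so what matters is that an observed event can become an observed zero. Because the clause decides which events count toward the primary objective, it should be settled before the Day 71 database freeze and group-level unblinding described in SAP 6.2.

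**What to change.** Reword Protocol 9.6.3 along these lines: *Data obtained before a subject leaves the study, whether or not consent is withdrawn, are retained, reported and analyzed. Withdrawal of consent ends further data collection only.*

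Mirror this in the SAP:

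- 6.3.1: a subject who withdraws consent after at least one immunization stays in the safety population with all data to that date.
- 6.6: the same rule applies to each PSRT summary.
- Disposition table: give the number of consent withdrawals, with reasons, by dose group, so that a reader can see whether the issue arose.

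Align the consent form with the new wording.

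The cost is one or two sentences in the protocol, a few lines in the SAP, and matching consent text, with the review that Protocol 15.1.2 requires for any modification. It adds no visits, samples or procedures.
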